#### Screening Period

The first visit will be a Screening Visit and will include a review of the inclusion/exclusion criteria (see Section 5.3). Subjects should undergo the Day 1 visit as soon as possible after eligibility for the trial has been confirmed. Subjects who do not meet all inclusion criteria or meet one or more of the exclusion criteria within the first Screening Period and are considered screen failures. If inclusion/exclusion criteria are not met at the end of the 28-day Screening Period (+ 7-day window), either the initial Screening Period or the single Rescreening Period, based on the results of the repeated tests, the subject should be considered a screen failure and not be enrolled in the study.

#### Rescreening:

Subjects who are considered screen failures after a first Screening Period may undergo rescreening once, after approval by the Medical Monitor (see Section 5.3). If a subject is rescreened, all screening tests will need to be repeated except as follows:

- a. Documented chest X-ray (CXR), hand and wrist X-ray if applicable, and TB testing must have occurred within 3 months of the initial rescreening visit, or need to be repeated during the Rescreening Period.
- b. Hepatitis and Human Immunodeficiency Virus (HIV) testing must have occurred within 1 month of the initial rescreening visit, or need to be repeated during the Rescreening Period.

#### Retesting:

During the initial Screening Period, or single Rescreening Period, testing may be repeated for subjects if test results, would preclude enrollment in the study, and are thought to represent a laboratory error or a reversible, clinically insignificant intermittent condition, or are inconsistent with the subject's historical values (see Inclusion Criteria 12 and 13 for specifics regarding tuberculosis [TB] testing), after discussion with the Medical Monitor. When a test needs to be repeated during the Screening Period, the Screening Period can be extended to 8 weeks after discussion with the Medical Monitor.

## Evobrutinib

### Phase IIb in Rheumatoid Arthritis MS200527-0060

---

In addition, if the initial MRI quality check at Screening indicates a repeat MRI is necessary, the Screening Period may be extended up to 7 days after discussion with the Medical Monitor.

#### **Treatment Period (Double-blind Placebo-controlled)**

The duration of the Treatment Period will be 12 weeks starting at randomization (Day 1). The Day 1 visit will be considered the Baseline for disease activity assessments (eg, ACR20/50/70, ACR hybrid, Disease Activity Score Based on a 28 Joint Count [DAS28], Clinical Disease Activity Index [CDAI], Simplified Disease Activity Index [SDAI]). Subject eligibility and a negative pregnancy test (if applicable) must be reviewed on Day 1 prior to randomization, and the first dose of IMP will be given while the subject is still on site for Day 1. Subjects must then return to the site for trial visits as indicated in the Schedule of Assessments [Table 1](#).

Treatment decisions will be made by Investigator assessment for the purpose of subject management.

Any subjects permanently withdrawn from IMP will be expected to complete the End of Treatment/Early Withdrawal Visit within 5 days of IMP withdrawal, followed by the Safety Follow-up Visit.

#### **Safety Follow-up Period**

Subjects will enter the Safety Follow-up Period after the Week 12/End of Treatment Visit. For subjects who discontinue the Treatment Period (discontinue IMP) during the main study, an End of Treatment/Early Withdrawal Visit should occur with the subject then entering the Safety Follow-up Period. The Safety Follow-up Visit/End of Trial visit is scheduled 28 days (+ 5-day window) after the End of Treatment/Early Withdrawal Visit.

#### **Assessment of Endpoints**

[figure not shown]
During the trial, clinical efficacy endpoints will be evaluated using several assessments, such as the ACR20/50/70, hybrid ACR, DAS28, CDAI, SDAI, and others. Efficacy in terms of prevention of joint structural damage progression will be assessed using MRI, scored using the Outcome Measures in Rheumatology Clinical Trials (OMERACT) Rheumatoid Arthritis Magnetic Resonance Imaging Scoring System (RAMRIS) and other MRI scoring systems. Efficacy in terms of physical function will be assessed using the Health Assessment Questionnaire – Disability Index (HAQ-DI). Effects of treatment on HRQoL will be examined using subject-reported outcome measures including but not limited to: Medical Outcomes Study 36-item Short Form Health Survey (SF-36v2) and FACIT-Fatigue.

Safety will be evaluated through the nature, occurrence, severity, and outcome of adverse events (AEs), and assessment of physical examination findings, ECGs, hematology and chemistry laboratory assessments, vital signs, and absolute values and change from Baseline in serum immunoglobulin (Ig) levels (IgA, IgG, IgM, and IgG subclasses) and total B cell counts.

#### **Statistical Methods**

Statistical methods including sample size justification are provided in Section 8.

Figure 1 Schematic of the Trial Design – Screening to Safety Follow-up Visit

ACR = American College of Rheumatology, ACR20 = ACR 20% Response Criteria, %ACR20-CRP = Proportion of subjects achieving an ACR20 response, where the acute phase reactant criterion is based on hsCRP, D1 = Day 1, MTX-IR = RA subjects with inadequate response to methotrexate, PO = Orally, RA = rheumatoid arthritis, SFU = Safety Follow-up Visit.

## 5.2 Discussion of Trial Design

### 5.2.1 Scientific Rationale for the Trial

The proposed Phase IIb trial design is based on experience with evobrutinib in the Phase IIa trial for RA (MS200527-0081), studies of other treatments for RA, consensus guidelines for treatment of RA (refer to American College of Rheumatology Guideline for the Treatment of Rheumatoid Arthritis [2015]), Food and Drug Administration (FDA) draft guidance (refer to FDA Guidance

## Evobrutinib

### Phase IIb in Rheumatoid Arthritis MS200527-0060

---

for Rheumatoid Arthritis: Developing Drug Products for Treatment [2013]), and European Medicines Agency (EMA) draft guidance (refer to EMA Evaluation of Medicines for Human Use: Points to Consider on Clinical Investigation of Medicinal Products Other Than NSAIDs for Treatment of Rheumatoid Arthritis [2015]).

#### Study Population

The proposed trial will evaluate RA subjects with inadequate response to MTX and no prior treatment with biologic DMARD (bDMARD) or targeted synthetic DMARD (tsDMARD [eg, JAK inhibitors, BTK inhibitors]), which we will refer to as the MTX-IR population. Subjects will be randomized to 1 of 3 doses of evobrutinib or placebo.

The MTX-IR population represents a well characterized segment of the total population of individuals with RA, and is one of the populations in which efficacy must be evaluated to obtain approval in the EU per EMA guidance.

Beyond assessing efficacy on clinical endpoints (eg, ACR20 response at 12 weeks, DAS28, ACR core set measures, ACR-EULAR remission), efficacy will also be assessed on physical function (HAQ-DI), pain (VAS), fatigue (FACIT-Fatigue), and HRQoL (SF-36), as these patient-reported concepts are relevant in patients' lives and treatment is expected to impact these variables. Efficacy in preventing structural damage progression will be assessed using MRI in the MRI substudy. Other than the inclusion/exclusion criteria for MRI substudy eligibility, participation in the MRI substudy is purely random, based on MRI availability at a particular site.

#### Endpoint Selection

The primary endpoint, ACR20 response at Week 12, is in accordance with FDA and EMA regulatory guidance documents for dose-ranging studies in RA. Clinical response will also be assessed using ACR50 response and ACR 70 response, as well as measures of low disease activity (LDA [eg, DAS28-CRP < 2.6]) and remission (eg, ACR/European League Against Rheumatism [EULAR] remission). Physical function will be assessed using HAQ-DI. Prevention of structural damage progression will be assessed using MRI at Weeks 4 and 12 in the MRI substudy.

#### Dose Range Finding

As all agents approved since the introduction of TNF antagonists in RA have used the same doses in patient populations with inadequate response to either MTX (MTX-IR) or to MTX and at least one bDMARD (bDMARD-IR), we will study the efficacy of evobrutinib with 3 doses in the MTX-IR to allow the assessment of dose response in this population, and will plan to evaluate the dose(s) identified on the basis of this study for subsequent development in all of the RA subpopulations to be studied (MTX-IR, bDMARD-IR, DMARD-naïve).

### Stratification Factors at Randomization

Subjects will be stratified by whether or not they are in the MRI substudy and by region to account for the impact on study outcomes of these factors.

### Use of Magnetic Resonance Imaging to Evaluate Joint Structural Damage Progression

Classically, joint structural damage in RA has been evaluated with radiographic methods, such as the modified Total Sharp Score (mTSS) (van der Heijde 2000). However, these methods are insensitive to early changes, requiring either 1- and 2-year study durations or large studies of shorter duration enriched for patients with documented erosions at Baseline, to assess the ability of an agent to prevent progression of joint structural damage. Due to these limitations, OMERACT developed the RAMRIS, which evaluates wrist and hand MRI images and scores them for erosions, synovitis, tenosynovitis, and osteitis (Ostergaard 2004, Ostergaard 2017). Unlike the mTSS, the OMERACT RAMRIS scores have been shown to be sensitive to changes as early as 12 weeks, and these changes predict radiographic progression as measured by the mTSS (Baker 2014, Baker 2016, Conaghan 2016, Genovese 2016b). Further, these changes have been shown to predict efficacy in longer studies using the mTSS. A validated 9-point scale for the assessment of cartilage loss (CARLOS) (Peterfy 2012) will also be used.

In the proposed trial, approximately 50% of the subjects will be evaluated using MRI to assess treatment effect on the MRI scores at 4 and 12 weeks when compared to Baseline, which we refer to as the MRI substudy. Barring subjects with contraindications to MRI imaging (eg, allergy to MRI contrast, presence of a non-MRI compatible metal medical device or foreign body), participation in the MRI substudy will be required for enrollment at MRI capable sites, in order to avoid selection bias. To ensure an adequate sample size in the MRI substudy, enrollment of non-MRI subjects may be capped. As the non-MRI subjects are projected to be recruited faster than the MRI subjects, capping recruitment of MRI subjects is unlikely to be required. However, if during the course of the study, it appears that MRI subjects will reach 45/arm in advance of the non-MRI subjects reaching 45/arm, we may limit enrollment of further MRI subjects to prevent over enrollment in the MRI substudy.

**Evobrutinib**

**Phase IIb in Rheumatoid Arthritis  
MS200527-0060**

**CCI**

Evobrutinib

Phase IIb in Rheumatoid Arthritis  
MS200527-0060

CCI

CCI

### 5.2.3 Rationale for Endpoints

#### 5.2.3.1 Primary Efficacy Endpoints

The ACR20 response at Week 12 is the primary efficacy endpoint.

## Evobrutinib

### Phase IIb in Rheumatoid Arthritis MS200527-0060

---

The endpoints and schedule for the efficacy assessments reflect the most updated FDA regulatory guidance and evidence-based recommendations for this indication. As the placebo-controlled period is limited to the first 12 weeks of the trial, due to ethical concerns regarding longer use of placebo in subjects given the availability of other approved, effective therapies (bDMARD and tsDMARD) for the MTX-IR population, the primary endpoint, ACR20, is assessed at 12 weeks ([American College of Rheumatology Clinical Trial Priorities and Design Conference 2010, Boers 2009](#)).

Efficacy in RA as evaluated in clinical trials is measured using the American College of Rheumatology Core Set of Disease Activity Measures for Rheumatoid Arthritis Clinical Trials ([Felson 1993](#)), commonly referred to as the ACR Core Set. The ACR Core Set consists of:

1. Swollen Joint Count (of 66 joints assessed)
2. Tender Joint Count (of 68 joints assessed)
3. Physician's Global Assessment of RA Disease Activity (generally assessed using a visual analog scale [VAS])
4. Acute Phase Reactant – erythrocyte sedimentation rate (ESR) or C-reactive protein (CRP)
5. Physical function (as assessed using the HAQ-DI or other validated instrument)
6. Pain (as assessed using the Patient's Assessment of Arthritis Pain VAS)
7. Patient's Global Assessment of RA Disease Activity

The definition of an ACR20 response, and many other assessments in RA (eg, ACR50, ACR70, CDAI, SDAI, DAS28, EULAR Responder Index), are calculated from evaluation of the ACR Core Set. Criteria for remission and LDA are also assessed using items from the ACR Core Set or indices derived thereof (eg, ACR/EULAR remission criteria,  $CDAI \leq 3.3$ ,  $DAS28 \leq 3.2$ ,  $SDAI \leq 3.3$ ).

**ACR20** – An ACR20 response, the most extensively used criterion for response in RA, is defined as an improvement of at least 20% in the number of tender joints and swollen joints, and at least 20% improvement in 3 out of the remaining 5 ACR core-set measures (patient pain, patient and physician's global assessment, physical function, acute phase reactants). ACR20 is the FDA-recommended efficacy endpoint for dose-ranging studies in RA in the FDA guidance, and is in line with EMA guidance for dose-ranging studies in RA. In this trial, the acute phase reactant for assessing ACR20 response for the primary endpoint is the high-sensitivity C-reactive protein (hsCRP).

## 5.2.3.2 Secondary Endpoints

### 5.2.3.2.1 Key Secondary Endpoints

#### 5.2.3.2.1.1 Efficacy

DAS28-hsCRP low disease activity (DAS28 < 3.2) rate, DAS28-hsCRP remission (DAS28 < 2.6) rate, and ACR50 and ACR70 responses at Week 12 are the key secondary efficacy endpoints.

**DAS28** – The DAS28 is a composite score derived from 4 measures (Aletaha 2008, Vander Cruyssen 2005). The components of DAS28 are:

- The number of swollen joints (out of the 28)
- The number of tender joints (out of the 28)
- Erythrocyte sedimentation rate or hsCRP
- Patient's Global Assessment of Disease Activity (0-10 scale).

In this study, DAS28-hsCRP will be used for determination of any endpoint that includes the DAS28 (eg, DAS28 remission, DAS28 LDA). DAS28-hsCRP is computed as follows, with hsCRP expressed in units of mg/L:

$$\text{DAS28-hsCRP} = 0.56 \times \sqrt{(\text{TJC28})} + 0.28 \times \sqrt{(\text{SJC28})} + 0.36 \times \ln(\text{hsCRP} + 1) + 0.014 \times \text{GH} + 0.96$$

Thresholds for disease severity grading, including remission, have been established for the DAS28 and other composite disease activity measures used in the assessment of RA (Anderson 2012), and are presented in Table 5 for the DAS28, CDAI, and SDAI.

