#### 7.3.1.4 Disease Activity Score - high-sensitivity-C-Reactive Protein

The DAS28-hsCRP is a measure of disease activity in 28 joints that consists of a composite numerical score of the following variables: TJC, SJC, hsCRP, and Patient's Global Assessment of Disease Activity ([Vander Cruyssen 2005](#)).

For DAS28-hsCRP, the 28 joints to be examined and assessed as tender or not tender for TJC and to be examined and assessed as swollen or not swollen for SJC include 14 joints on each side of the subject's body: 2 shoulders, 2 elbows, 2 wrists, 10 MCP joints, 2 interphalangeal joints of the thumb, 8 proximal interphalangeal joints, and 2 knees ([Smolen 1995](#)).

In this trial, the acute phase reactant for computing DAS28 is the hsCRP. DAS28-hsCRP will be derived using the following formula from the DAS28 website ([DAS 2016](#)):

$$DAS28-hsCRP = 0.56 \times \sqrt{(TJC28)} + 0.28 \times \sqrt{(SJC28)} + 0.014 \times GH + 0.36 \times \ln(hsCRP + 1) + 0.96$$

Where:

- TJC28 = 28 joint count for tenderness
- SJC28 = 28 joint count for swelling
- $\ln(\text{hsCRP})$  = natural logarithm of hsCRP
- GH = the general health component of the Disease Activity Score (DAS) (ie, Patient’s Global Assessment of Disease Activity).

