### 7.3.1.5 Clinical Disease Activity Index

The CDAI is calculated based on the following formula (Smolen 2014):

$$CDAI = SJC28 + TJC28 + GH + PhGA$$

Where:

- TJC28 = 28 joint count for tenderness
- SJC28 = 28 joint count for swelling
- GH = the general health component of the DAS (ie, Patient’s Global Assessment of Disease Activity on a 100-mm horizontal VAS, where the left end represents “very well”, and the right end represents “very poor”, converted to a cm scale [0 to 10 cm]).
- PhGA = Physician’s Global Assessment of Disease Activity on a 100-mm horizontal VAS, where the left end represents “very well”, and the right end represents “very poor”, converted to a cm scale (0 to 10 cm).

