### 7.3.1.7 Visual Analog Scales

Visual analog scales will include the patient's assessment of pain, the patient's assessment of disease activity, and the physician's assessment of disease activity. Patient-reported outcome questionnaires must be performed prior to any other assessments at all visits.

**Patient's Assessment of Arthritis Pain:** The subject's assessment of his or her current level of pain related to arthritis over the previous 7 days will be recorded using the 100-mm horizontal VAS where the left end represents "no pain" and the right end represents "severe pain." The scale should be administered prior to the tender and swollen joint count examination.

**Patient's Global Assessment of Disease Activity:** The subject's overall assessment of his or her disease activity during the last 24 hours will be recorded using a 100-mm horizontal VAS, where the left end represents "very well", and the right end represents "very poor." The subject will be asked "considering all the ways that your arthritis affects you, draw a single vertical line (|) through the line below to indicate how your arthritis is today."

**Physician's Global Assessment of Disease Activity:** The Investigator's assessment of the subject's current arthritis disease activity will be recorded using a 100-mm horizontal VAS, where the left end represents "no arthritis activity", and the right end represents "extremely active arthritis."

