**Table 8: Disease History**

Disease History Characteristics	Modalities
Time (months) since confirmed diagnosis of RA according to 2010 ACR/The EULAR RA classification criteria.	
 
• Summary statistics will be presented.
 
• Time will be computed as <math>(\text{Date of Informed Consent Signature} - \text{Date of confirmed diagnosis of RA}) / 30.4375</math>. If the date of confirmed diagnosis of RA is entirely missing, then time since confirmed diagnosis of RA will not be computed. In case of partial missing date of confirmed diagnosis of RA, this date will be imputed as follows:               
 
○ If only the day is missing, then it will be replaced by the first day of the month
 
○ If both day and month are missing, then it will be replaced by the first of January
 
 
 

Components from the ACR Core Set:
 
 
• Tender Joint Count ([TJC] among the 68-joint count),
 
• Swollen Joint Count ([SJC] among the 66-joint count),
 
• Subject's Global Assessment of Disease Activity (100-mm VAS),
 
• Subject's Assessment of Pain (100-mm VAS),
 
• HAQ-DI total score,
 
• Physician's Global Assessment of Disease Activity (100-mm VAS),
 
• hsCRP (mg/L)
 
	
 
• Summary statistics
 

Erythrocyte sedimentation rate (ESR) (mm/Hr)
	
By category (based on local normal ranges collected in electronic case report form [eCRF]):
 
 
• Low
 
• Normal
 
• High
 

hsCRP (mg/L)
	
By category:
 
 
• Normal
 
• High
 

Acute-phase reactant
	
At least one test result is needed for the classification:
 
 
• Normal hsCRP and normal ESR,
 
• Abnormal hsCRP or abnormal ESR
 
 
Abnormal refers to either low or high normal range classification.

Rheumatoid factor (RF) (expressed in IU/mL)
	
By category:
 
 
• Negative (<math>\leq</math> Upper Limit of Normal [ULN])
 
• Positive (<math>></math> ULN)
 

Serum Ig levels (IgG, IgA, IgM) (mg/dL)
	
By category:
 
 
• Negative (<math>\leq</math> ULN)
 
• Positive (<math>></math> ULN)
 

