## 18 Appendices

### 18.1 Definitions of Efficacy Endpoints

**ACR20** - The ACR20 is a primary efficacy measure for which a subject must have at least 20% improvement in the following ACR Core Set values:

- TJC (being the number of joints assessed as “Pain/Tender only” or “Pain/Tender and Swollen” among the 68-joint count) and
- SJC (being the sum of joints assessed as “Swollen only” or “Pain/Tender and Swollen” among the 66-joint count) and
- An improvement of at least 20% in at least 3 of the following 5 assessments:
  - Subject’s Global Assessment of Disease Activity
  - Subject’s Assessment of Pain
  - Subject’s Assessment of Physical Function as measured by the HAQ-DI
  - Physician’s Global Assessment of Disease Activity
  - Acute phase reactant as measured by hsCRP.

In this trial, ACR20 response calculations will use the HAQ-DI for the subject’s assessment of physical function and hsCRP as the measure of acute phase reactant.

Improvement of at least 20% of these assessments is defined as follows:

- TJC (68 joint count): a decrease of at least 20% of the number of tender joints compared to baseline
- SJC (66 joint count): a decrease of at least 20% of the number of swollen joints compared to baseline
- Subject's Global Assessment of Disease Activity: a decrease of at least 20% on the VAS compared to baseline. *Note: The scale has been scored from 100 [very well] to 0 [very poor] during the data collection. As a result, for analyses, the parameter is derived as 100 – the original value to correctly assess the subject's global assessment of disease activity and calculate the improvement from baseline.*
- Subject's Assessment of Pain: a decrease of at least 20% on the VAS compared to baseline.
- Subject's Assessment of Physical Function: a decrease of at least 20% of the HAQ-DI score compared to baseline.
- Physician's Global Assessment of Disease Activity: a decrease of at least 20% on the VAS compared to baseline
- Acute phase reactant: a decrease of at least 20% of hsCRP measurement compared to baseline

**ACR50, ACR70** - ACR50 and ACR70 are defined in the same way as the ACR20 using at least 50% and 70% improvement, respectively.

**DAS28-hsCRP** - The DAS28-hsCRP is a measure of disease activity in 28 joints that consists of a composite numerical score of the following variables: TJC, SJC, hsCRP, and Patient's Global Assessment of Disease Activity ([Vander Cruyssen 2005](#)).

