**SDAI** – The SDAI is the numerical sum of 5 outcome parameters: TJC and SJC (based on a 28-joint assessment), the Patient’s and the Physician’s Global Assessments of disease activity (0–10 cm VAS), and level of CRP (expressed in units of mg/dL). The SDAI is a valid and sensitive assessment of disease activity (Aletaha 2005, Smolen 2014) and treatment response that is comparable with the DAS28 and ACR response criteria; it is easy to calculate and therefore a viable tool for day-to-day clinical assessment of RA treatment (Fransen 2005, Smolen 2014). The ACR/EULAR 2011 Index-based definition of remission is based on SDAI (SDAI ≤ 3.3), and is being assessed as a secondary endpoint (Felson 2011, Smolen 2014).

**CDAI** – The CDAI is a composite index (without acute-phase reactant) for assessing disease activity. CDAI is based on the simple summation of the count of SJC and TJC of 28 joints along with the Patient’s and Physician’s Global Assessments (0–10 cm VAS) for estimating disease activity. The greater advantage associated with CDAI is its potential to be employed in evaluation of subjects with RA consistently with close frequency and independently of any calculating device; therefore, it can essentially be used everywhere and anytime for disease activity assessment in subjects with RA (Aletaha 2005, Smolen 2014). Thresholds for disease severity grading are included in Anderson (Anderson 2012). Remission based on CDAI is also being assessed as a secondary endpoint.

**EULAR/ACR Boolean Remission** – Following the Boolean-based definition of remission of ACR/EULAR, at any time point, a subject must satisfy all of the following: tender joint count TJC ≤ 1, SJC ≤ 1, CRP ≤ 1 mg/dL and Patient’s Global Assessment ≤ 1 (on a 0–10 scale). The Patient’s Global Assessment must be elicited as follows: “Considering all of the ways your arthritis has affected you, how do you feel your arthritis is today? (0–10, where 0 = very well and 10 = very poorly)”. The Boolean criteria appear more stringent than the DAS28 remission and have been specifically created for use in clinical trials (Bykerk 2012, Felson 2011).

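### The protocol gives the DAS28 patient global a 0-10 scale beside a coefficient of 0.014, although the item is a 100-mm VAS, and the SAP does not say which scaling enters DAS28

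*Protocol*

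**What the plan says.** **Protocol**

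- Section 5.2.3.2.1.1 lists the four DAS28 components and gives the patient one as "Global Assessment of Disease Activity (0-10 scale)". The formula that follows contains 0.014 × GH. The only unit stated with the formula is for CRP: "with hsCRP expressed in units of mg/L".
- Section 7.3.1.4 repeats the formula with "GH = the general health component of the Disease Activity Score (DAS)". It identifies GH as the patient global and gives no scale.
- Section 7.3.1.5 (CDAI) uses the same symbol GH for the patient VAS "converted to a cm scale [0 to 10 cm]". Section 7.3.1.6 (SDAI) does the same.
- Section 7.3.1.7 says that the item "will be recorded using a 100-mm horizontal VAS".

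**SAP**

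- Table 8 lists the variable as "Global Assessment of Disease Activity (100-mm VAS)".
- Appendix 18.1, under ACR20, notes that "The scale has been scored from 100 [very well] to 0 [very poor] during the data collection" and that the analysis value is 100 minus the collected one.
- Appendix 18.1, under CDAI, uses "Global Assessments (0–10 cm VAS) for estimating disease activity". SDAI and Boolean remission are also on 0-10.
- Appendix 18.1, under DAS28-hsCRP, repeats the formula and defines GH as the patient global. It states no scale for GH and no unit for hsCRP.

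**The concern.** Section 5.2.3.2.1.1 is the only DAS28 definition in either document that attaches a scale to the patient global, and that scale conflicts with the instrument. The coefficient is the same in all three places, so the scale decides whether this term can contribute up to 1.40 points or up to 0.14.

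A programmer who takes the 0-100 analysis variable gets the score that was probably meant. One who follows Section 5.2.3.2.1.1, or reuses the cm value already derived for CDAI and SDAI under the same symbol, gets a lower score for every subject with a global above zero. No error message would appear, and the values would still look plausible.

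Two of the four key secondary efficacy endpoints are proportions below fixed DAS28 cut-offs (3.2 and 2.6). Change in DAS28, EULAR response and the baseline DAS28 categories in SAP Table 8 use the same score.

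**Working it through.** **Inputs.** The formula in Protocol 5.2.3.2.1.1, Protocol 7.3.1.4 and SAP 18.1 is

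DAS28-hsCRP = 0.56√TJC28 + 0.28√SJC28 + 0.36 ln(hsCRP + 1) + 0.014 GH + 0.96.

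The cut-offs are 3.2 and 2.6 (Protocol 8.3.2). The EULAR change thresholds are 0.6 and 1.2 (Protocol Table 7).

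**1. The documents' own ranges (Protocol Table 5).**

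- The CDAI range reproduces exactly with both globals on 0-10: 28 + 28 + 10 + 10 = 76.
- The SDAI range of 86 then leaves 10 mg/dL, that is 100 mg/L, for CRP.
- With 28 tender joints, 28 swollen joints and hsCRP of 100 mg/L, the DAS28 maximum is 2.963 + 1.482 + 1.661 + 0.96 = 7.066 plus the GH term. This gives 8.47 with GH = 100 (+1.40) and 7.21 with GH = 10 (+0.14).
- Table 5 states 0 to 9.4. Neither scaling reproduces it, and the formula's minimum is 0.96, not 0. The 0-100 scaling comes closer, but this is weak evidence, because the Table 5 row is not limited to the CRP version of DAS28.

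**2. Size of the shift.** For a global of g mm, the two scalings differ by 0.014g − 0.014g/10 = 0.0126g.

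| Global (mm) | DAS28 lowered by | Counted as < 3.2 if the mm-scale score is below | Counted as < 2.6 if the mm-scale score is below |
|---|---|---|---|
| 20 | 0.252 | 3.45 | 2.85 |
| 40 | 0.504 | 3.70 | 3.10 |
| 60 | 0.756 | 3.96 | 3.36 |

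The band between the cut-offs is 3.2 − 2.6 = 0.6 wide, and 0.6/0.0126 = 47.6 mm. Above that global, a subject with moderate activity on the mm scale can be counted in remission.

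**3. Worked subjects (values assumed).**

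- TJC28 2, SJC28 2, hsCRP 5 mg/L, global 40 mm: 0.792 + 0.396 + 0.645 + 0.96 = 2.793. Adding 0.56 gives 3.35 (not low disease activity); adding 0.056 gives 2.85 (low disease activity).
- TJC28 1, SJC28 1, hsCRP 5 mg/L, global 60 mm: 0.56 + 0.28 + 0.645 + 0.96 = 2.445. Adding 0.84 gives 3.29 (moderate); adding 0.084 gives 2.53 (remission).

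**4. Change scores.** A 40 mm improvement in the global contributes 0.014 × 40 = 0.56 on 0-100 and 0.014 × 4 = 0.056 on 0-10. On 0-10 the component's whole range is 0.14, which is 0.14/0.6 = 23% of the smaller EULAR threshold.

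**5. Direction of the effect on the treatment difference.** The documents give no Week 12 distributions, so this step only asks whether the direction is fixed. It used 400,000 simulated subjects per arm with independent components, all inputs assumed:

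- joint counts negative binomial, shape 1.5, capped at 28
- hsCRP lognormal, log SD 0.9
- global normal, SD 22, clipped to 0-100

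| Scenario: mean TJC28 / mean SJC28 / median hsCRP / mean global | Difference in low-disease-activity rate, GH 0-100 | Same, GH 0-10 |
|---|---|---|
| All components improve: control 9/6/12/50, active 5/3.5/7/35 | 19.1 points | 28.6 points |
| Only the global improves: control 6/4/8/50, active 6/4/8/30 | 7.7 points | 1.4 points |

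The difference can grow or shrink. These figures are not estimates for this trial.

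**The case against.** The strongest reply is that the 0-10 wording sits in a rationale section that describes DAS28 in general terms, and that neither Protocol 7.3.1.4 nor the SAP repeats it. On this view the SAP as a whole points to 0-100. The item is a 100-mm VAS, the note on reversing the score is worded for analyses in general, and a 0-10 value is stated only where one is used (CDAI, SDAI, Boolean remission). Harm then requires a programmer to take the less natural reading, and nothing shows that this happened.

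Much of this stands. The balance of the SAP does favour 0-100, the harm is conditional, the Table 5 check is weak, and the simulated figures show only that the direction is open. A separate symbol for the cm-scaled global is tidying.

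It does not remove the point. The same rationale section states how the score is computed in this study, and it is the only place that gives the hsCRP unit for the formula, so it is hard to set aside for the patient global alone. The sections that should settle the matter are silent. The reversal note appears under ACR20, not DAS28. Reaching 0-100 requires the reader to override the only scale written for this score.

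**Conclusion.** The concern holds. Protocol 5.2.3.2.1.1 states a scale that does not fit the instrument or, on the likely intent, the coefficient, and SAP 18.1 does not say which of its two scalings applies. That 0-100 is intended is an inference, mainly from the 100-mm VAS and from the SAP's use of 0-10 only for other indices.

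If the 0-10 value were used, each DAS28 would fall by 0.0126 per mm of patient global, and the low-disease-activity and remission rates would stay the same or rise in every arm. That result needs no distributional assumption. How many subjects would be reclassified, and which way the difference from placebo would move, cannot be determined from the documents.

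The reach is limited. ACR20 and its Hochberg control are untouched, and SAP 14.2 treats the secondary analyses as supportive with nominal p-values. The correction should be made before the endpoints are programmed; it does not threaten the primary conclusion.

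**What to change.** - **SAP 18.1, DAS28-hsCRP:** state that GH is the derived patient global on 0-100 mm (100 minus the collected value) and that hsCRP is in mg/L. Add that the same derived variable divided by 10 is used for CDAI, SDAI and Boolean remission.
- **Protocol 5.2.3.2.1.1:** correct the 0-10 scale in the component list.
- **Protocol 7.3.1.4:** state the unit of GH.
- **Protocol 7.3.1.5 and 7.3.1.6 (optional):** use a different symbol for the cm-scaled global.

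The SAP change alone settles the analysis. The cost is two sentences in the SAP and a non-substantial protocol correction, with no new data. If the programs already use 0-100, no result changes.
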